Statistical methods	
Primary and secondary endpoints:
 
A primary and 2 supplementary estimands will be defined for the primary endpoint, change in EASI from baseline to Week 16, in order to assess different clinical questions of interest.
 
 • The primary estimand for the primary endpoint will use the hypothetical strategy to handle the occurrence of pre-defined intercurrent events (initiation of rescue treatment and permanent discontinuation of IMP). • A first supplementary estimand will use the treatment policy and hypothetical strategies to account for the occurrence of intercurrent events. • A second supplementary estimand will use the composite and hypothetical strategies to handle the occurrence of intercurrent events. 
For the main analysis of the primary estimand, data observed after the occurrence of an intercurrent event will be excluded from the analysis. Missing data will be assumed to be MAR. The primary endpoint will be analyzed using an MMRM including treatment, visit, visit by treatment interaction terms, and region (Japan, non-Japanese countries) as factors, and adjusting for the baseline EASI score as a covariate. The covariance matrix will be assumed to have an unstructured form and the Kenward-Rodger approximation will be used to estimate the denominator degrees of freedom.
 
To explore the exposure-response relationship, the change in EASI score from baseline to Week 16 will be assessed based on an ANCOVA model including region as a factor and C_{trough} at Week 16 and baseline EASI score as covariates. Data observed after the occurrence of an intercurrent event will be excluded and missing data will be assumed to be MAR.

	The secondary endpoint, number of AEs from baseline to Week 16+3 days per subject, will be reported descriptively by treatment group.
Signatory investigator	PPD [REDACTED], MD PPD [REDACTED] [REDACTED] Hannover, Germany
Sponsor	LEO Pharma A/S, [name]

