5.2.1 Nonclinical data

LEO 152020 binds selectively to human H4R and has been characterized as antagonist, inhibiting the histamine-induced effects of the H4R. CCI [REDACTED]

In safety pharmacological studies, LEO 152020 did not have any neurobehavioral and respiratory effects. Oral dosing in monkeys at dose levels up to CCI mg/kg did not result in any changes in body temperature, blood pressure, or heart rate, and there were no clinical signs of AChE inhibition. ECG monitoring showed a CCI [REDACTED] at doses CCI mg/kg with no biological significance in the monkey.

Ex vivo and in vivo models have shown that LEO 152020 has CCI efficacy and in addition has CCI in several models of pruritus in mice.

In a 26-week rat toxicology study, histopathological investigation showed an CCI CCI in the CCI compared with their control. CCI were also observed and considered secondary to the findings in the CCI. These findings were observed at the highest dose level tested (CCI) and were partially reversed after a CCI recovery period. In this study, NOAEL was CCI mg/kg/day for CCI corresponding to a safety margin of CCI and an exposure margin of CCI to the therapeutic dose of LEO 152020 CCI.

The pharmacokinetic profile of LEO 152020 was investigated in mice, rats, and monkeys. The main route of elimination was urinary and the unchanged parent compound was the

predominant component in all urine, feces, and plasma. No metabolites observed were >5% of the dose administered. LEO 152020 was evaluated to be non-genotoxic and with no phototoxic potential. Repeated-dose studies in rats and monkeys up to 16 weeks revealed a toxicity profile amenable to clinical monitoring and of low concern for human risk and provided adequate safety margins.

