Nocturnal [CCI] and sleep [CCI] monitoring by wristband actigraphy is not considered to bear a risk (Section 11.7.2). A hypoallergenic bandage can be placed under each of the wristband actigraphy devices to prevent skin irritation on the wrists.

Risks for subjects treated with LEO 152020

Due to the important potential risk of [CCI], the dose regimens explored in this trial have been chosen to minimize that risk for the subjects. The highest dose regimen in the trial ([CCI]) is predicted to result in concentration levels below those of the [CCI] mg once daily dose regimen, which in the first-in-human trial resulted in a mean [CCI] of [CCI] with an upper bound of the 90% CI for [CCI] ([CCI]) at [CCI] (Section 5.2.2). Since subjects with mild and moderate renal impairment may exhibit increased exposure of LEO 152020, ECGs will be measured at each visit (Section 4) to monitor the individual subjects in line with [CCI] for drugs for which a [CCI] cannot be excluded (Panel 2).

To further ensure subject safety, subjects with cardiac arrhythmic risk factors, moderate and severe hepatic impairment, and/or severe renal impairment will be excluded from participation in the trial (Section 8.3). Subjects using medications for which [CCI] is a known side effect and which cannot be replaced by safe alternative medication(s) will be excluded from participation in the trial (Section 9.7). Moreover, medications known to inhibit the [CCI] [CCI], and/or [CCI] will be prohibited during the trial (Section 9.7 and Appendix 8). Frequent ECG monitoring will be conducted with pre- and/or post-dose ECGs measured and evaluated at the sites and centrally (Section 11.4.3). At selected visits, ECG and PK blood samples collected at the same timepoint will be used to explore the relation between exposure of LEO 152020 and potential [CCI] (Section 4). In the multiple dose part of the first-in-human trial, a dose-dependent [CCI] in heart rate was observed with a [CCI] [CCI] ([CCI]) in the [CCI] dose group. If a subject develops [CCI] and [CCI], the risk of [CCI] may increase. To mitigate this, ECGs will be taken at each visit (Section 4) to monitor all subjects.

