8.3 Exclusion criteria

Subjects are not eligible for the trial if they violate any of the following criteria:

1. Concurrent skin disease at baseline which may interfere with the trial assessments, at the discretion of the investigator.
2. Active skin infection or any other clinically apparent infection at baseline which may interfere with the trial assessments, at the discretion of the investigator.
3. Previous treatment with an oral H4R antagonist (including LEO 152020) within 6 months prior to baseline.
4. Previous treatment with 3 or more systemic AD treatments prior to screening.
5. Systemic treatment including systemic corticosteroids known or suspected to have an effect on AD within 4 weeks or 5 half-lives prior to baseline, whichever is longer.
6. Phototherapy within 4 weeks prior to baseline.
7. Positive HBsAg, anti-HBs*, anti-HBc, or HCV serology at screening.

*Subjects with positive anti-HBs are eligible provided that they have a negative HBsAg, negative anti-HBc (blood pattern in vaccinated subjects), and negative HCV serology.

8. Current active tuberculosis based on test per local standard at screening. The screening for tuberculosis should be done according to guidelines for patients subject to biologic treatment as per local standard of care.
9. Infection with HIV.
10. History of lymphoproliferative disease or malignancy (except treated and recovered non-melanoma skin cancer or cervical carcinoma in situ) within 5 years prior to screening.

11. Subjects at risk for Torsade de Pointes based on any of the following:
 - a. Uncorrected hypokalemia or hypomagnesemia at Week -1, history of cardiac failure, history of clinically significant/symptomatic bradycardia.
 - b. **CCI** or family history of idiopathic sudden death.
12. Use within 5 half-lives prior to screening of concomitant medication for which **CCI** is a known side effect and which cannot be discontinued or replaced by (a) safe alternative medication(s).
13. Resting QTcF (average of a triplicate measurement) <300 ms or >450 ms (men) or >460 ms (women) at screening.
14. Known history of ventricular arrhythmias.
15. Second- or third degree- atrioventricular block.
16. Subjects with severe renal impairment as determined by eGFR levels below 30 mL/min at screening (37). For eGFR levels allowed in Germany and Japan, see [Appendix 4](#).
17. Subjects with medical history of chronic moderate to severe liver disease.

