9.8.4 Accountability of the investigational medicinal products

The investigator is fully responsible for the IMPs at the trial site and for maintaining adequate control of the IMPs and documenting all transactions with them.

The IMP will be dispensed to the subject using an IRT system. Dispensing of the IMP may be delegated, e.g. to a hospital pharmacy, as locally applicable and must be documented in the Site Signature and Designation of Responsibility Log.

At each visit after baseline, the subject will be asked to return all (partly) used and unused IMP kits. Returned IMP need not be stored at the trial site at the storage temperature specified in Section 9.8.3 but must be stored separately from non-allocated IMP.

All returned IMP kits will fully be accounted for by the site staff in the IRT system (see separate trial product handling manual for more information). The IRT system will also maintain the inventory status of all IMP kits at the trial site (see separate IRT manual for more information on how to update kit status in the IRT system).

All returned IMP tablets will fully be accounted for by the site staff. Documentation of IMP accountability must be kept for the IMP dispensed to each subject randomized in the trial. This documentation must be available during monitoring visits and will be checked by the CRA to verify correct dispensing of the IMPs.

Reporting in eCRF

It will be recorded in the eCRF how many morning doses and how many evening doses of IMP were taken from the dispensed kit.

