14.3.8.4 Exposure-response modeling of LEO 152020

To explore the exposure-response relationship of LEO 152020, the change in EASI score from baseline to Week 16 will be assessed based on an ANCOVA model, including the C_{trough} values at Week 16 and the baseline EASI score as covariates and region (Japan, non-Japanese countries) as a factor. Data observed after the occurrence of an intercurrent event, will be excluded from the analysis and "treated as missing". Week 16 data, that is either missing or "treated as missing" due to the occurrence of an intercurrent event, will be assumed to be missing at random. The difference in the LS-mean change in EASI score from baseline to Week 16, based on the observed margins, along with the associated 95% CIs and nominal p-values will be presented. In case a linear relationship between change in EASI from baseline to Week 16 and C_{trough} cannot be shown, alternative models such as non-sigmoidal (with a hill coefficient =1) E_{max} or sigmoidal E_{max} will be considered. Further details regarding the goodness of fit criteria and the non-linear model will be described in the SAP.

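### The exposure-response slope on observed Week 16 trough can be biased in either direction: trough is not fixed by randomisation, and the model adjusts only for region and baseline EASI

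*Combined protocol and SAP*

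**What the plan says.** The synopsis (Statistical methods) specifies "an ANCOVA model including region as a factor and C_{trough} at Week 16 and baseline EASI score as covariates". Section 14.3.8.4 repeats the model, "including the C_{trough} values at Week 16 and the baseline EASI score as covariates and region (Japan, non-Japanese countries) as a factor", with confidence intervals and nominal p-values. Data after an intercurrent event are dropped and the resulting gaps are assumed missing at random. If linearity cannot be shown, Emax-type models in trough are considered; the SAP is to give the goodness-of-fit criteria and the non-linear model. Neither place has a term for randomised dose, renal function or compliance.

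On what moves trough besides regimen:

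- **Renal function.** Section 5.2.1 reports for the animal species: "The main route of elimination was urinary". Section 5.5 says that "subjects with mild and moderate renal impairment may exhibit increased exposure of LEO 152020". Exclusion criterion 16 removes only "Subjects with severe renal impairment as determined by eGFR levels below 30 mL/min at screening", except in Germany and Japan, where Appendix 4 sets the limit at 90 mL/min.
- **Home dosing.** By Section 9.2 and the footnotes to Panel 2, the dose behind the Week 16 trough is taken at home on the evening before the visit.
- **Who stays in.** Section 14.3.8 counts only rescue treatment and permanent discontinuation of IMP as intercurrent events. Section 14.3.3, writing about the pandemic, says that interruption of IMP is not one.

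Section 14.3.7 calls the exposure-response work exploratory, and it is not part of the gatekeeping procedure. It is nevertheless named first in the primary objective (Section 6), and Sections 5.3 and 12.1 tie the trial to choosing doses for later development.

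**The concern.** Randomisation protects comparisons between regimens. It does not protect a comparison between subjects with high and low trough inside one regimen, and the planned slope mixes the two. Anything that moves trough within an arm and is also tied to EASI change will enter the slope as if it were a drug effect.

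Two routes are open. A subject who sees no benefit may skip tablets without formally stopping; that subject contributes a low trough and a poor EASI result, with the arrow running from response to exposure. A subject who has cleared may also skip tablets, and that pushes the slope the other way. Separately, renal function shifts trough, and if it is related to EASI change by some path other than the drug, it confounds the slope. The region factor cannot stand in for renal function, because Germany (limit 90 mL/min) is pooled with non-Japanese countries where eGFR down to 30 mL/min is admitted.

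The stake is the reading of dose. The power simulation in Section 14.1 assumes the same response in all active arms. If that were true, a slope produced by adherence could still suggest that exposure matters, and a bias of the opposite sign could hide a real gradient.

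**Working it through.** **1. The plan's own figure.** None is given for the slope. The nearest is Panel 17: marginal power 90.8%, 85.3% and 85.3% for the regimen-versus-placebo contrasts. Allocation 4:3:3:4 of 224 gives 64, 48, 48 and 64. With 64 v 64, 90.8% power implies a standardised difference of (1.960 + 1.329) × √(2/64) = 0.581. At 48 v 64 that gives Φ(0.581/√(1/48 + 1/64) − 1.960) = Φ(1.08) = 86.1%, close to the stated 85.3%. Panel 17 is coherent on this check, but it concerns randomised contrasts and says nothing about the slope.

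**2. How little correlation is needed.** Suppose the drug does nothing and trough has residual correlation r with EASI change. The slope t-test then has non-centrality r/√(1 − r²) × √n on n − 4 degrees of freedom, two-sided at 5%. For the 160 active subjects:

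- r = 0: 5%
- r = 0.1: 0.1005 × 12.65 = 1.27, rejection 24%
- r = 0.2: 0.2041 × 12.65 = 2.58, rejection 73%

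If 15% of subjects are assumed lost (n = 160 × 0.85 = 136), the last two become 21% and 66%.

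**3. Null simulation of the planned ANCOVA** (2,000 trials per row, no drug effect). From the documents: arm sizes and SD 4.35 = √18.9, the residual variance Section 14.1 gives for one baseline-severity group. Assumed, because doses and PK are redacted:

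- relative doses 1:2:4;
- log-trough SD 0.5, of which renal function contributes 0.3;
- about 20% of last doses missed, each cutting trough to 25%.

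The plan does not say whether placebo subjects enter at trough zero, so both versions were run.

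| Assumed link with EASI change | Trough slope, placebo at 0 | Trough slope, active only | Randomised-dose slope (same two sets) | Mean trough slope, active only (EASI points per SD of trough) |
|---|---|---|---|---|
| None; renal function and missed doses move trough only | 6.1% | 4.5% | 5.6%, 5.0% | 0.01 |
| Poorer renal function, worse EASI change (0.3 SD) | 16.6% | 21.6% | 5.1%, 5.0% | +0.42 |
| Poor responders miss the last dose more (log-odds 0.5 per SD) | 13.0% | 16.6% | 4.9%, 5.5% | −0.34 |
| Same, log-odds 1.0 | 38.7% | 47.0% | 4.8%, 4.4% | −0.66 |
| Renal 0.3 SD and missed doses 0.5 together | 4.5% | 4.8% | 5.4%, 5.5% | +0.04 |

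Monte Carlo error at 5% is √(0.05 × 0.95/2,000), about 0.5 points. A negative slope is a false benefit of exposure; a positive one masks benefit. The worst row equals 0.66/4.35 = 0.15 SD of EASI change per SD of trough, so no extreme association is needed. Point sizes scale with the residual SD: at an assumed SD of 10, 0.34 and 0.66 become 0.79 and 1.51.

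**4. Adjusting for missed doses.** Under the null, a trough model that also had randomised dose, renal function and the missed last dose rejected 4.5% to 5.8%. That test flatters the adjustment, because there is no effect to lose. When the drug was given a real effect, adjustment for missed doses pulled a slope of about −3.2 to −2.5 and −2.1 in one simulation, and a slope of about −3.1 to between −2.7 and −2.3 in another. The losses are 1 − 2.5/3.2 = 22%, 1 − 2.1/3.2 = 34%, 1 − 2.7/3.1 = 13% and 1 − 2.3/3.1 = 26%.

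**The case against.** The sponsor has a fair answer on several counts.

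- **Status.** The analysis is declared exploratory, the protocol never says trough is randomised or the slope causal, and the three regimens are each compared with placebo as randomised, with intervals at every visit (Section 14.3.8.1). This stands, and it limits the weight of the point. A reader might infer that the efficacy conclusions are affected; they are not. But three contrasts with placebo are not a gradient across regimens, and nothing in the plan sets the trough slope beside a randomised one.
- **Renal route.** The documents support the link from renal function to exposure and are silent on any link to EASI change apart from the drug. This stands. A reader might infer that admitting renal impairment biases the slope by itself; the first row of the table shows about 5%.
- **Adherence route.** No skipping rates are documented, and there are safeguards: tablet counts and reminders (Section 9.8.5), supervised morning doses at visits up to Week 14, and removal of data after rescue or permanent discontinuation. These reduce the problem but do not reach the home doses that drive the Week 16 trough.
- **Direction.** A reader might infer that higher exposure would be falsely favoured. The direction is not fixed, and opposing mechanisms can cancel, as the last row of the table shows.
- **SAP.** No separate SAP text was available here, so further sensitivity analyses cannot be ruled out. What Section 14.3.8.4 expressly leaves to the SAP does not include covariates or a dose-based comparison.

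**Conclusion.** The point holds as a limited one. As specified, the trough slope is open to bias in either direction, most plausibly through missed doses that follow response, and through renal function only if an undocumented second link exists. Its size cannot be derived from the documents. Under the assumptions above, the null rejection rate runs from about 5% (no confounding, or cancelling mechanisms) to well above 20%, with 47% the highest in the table; these figures show what is possible and do not forecast this trial. The slope on randomised dose stayed between 4.4% and 5.6% throughout without any confounder being measured.

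The gatekept tests are unaffected. The point deserves action because exposure-response is half of the primary objective and is meant to help inform dose selection, and because the remedy uses data already collected.

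It is also tempting to conclude that compliance should simply be added to the model, since the eCRF records "how many morning doses and how many evening doses of IMP were taken from the dispensed kit". That does not follow: missed doses can be a consequence of response, and conditioning on them weakened a true slope by 13% to 34% in the checks above.

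**What to change.** Amend Section 14.3.8.4 and the synopsis, or fix it in the SAP before the randomisation code is broken:

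1. Add baseline covariates already collected to the trough model: screening eGFR or creatinine, body weight, age and sex. This addresses the renal route only.
2. Pre-specify beside it a slope on randomised dose or on arm-mean trough. State which scale is used and whether placebo subjects enter at zero. This slope uses only differences created by randomisation, plus the missing-at-random assumption the plan already makes.
3. State that the trough slope counts as evidence on dose only in the light of the randomised slope. Do not require both to agree: the randomised slope is less precise, and a strict rule could discard a true relationship.
4. Do not adjust for missed doses as a correction. Report them at most descriptively, next to the compliance summary in Section 14.3.6.

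The cost is a few lines of text and two model fits on existing data. The randomised-dose slope has about 1.5 to 1.7 times the standard error of the trough slope under the assumed inputs, so its confidence interval is wider by the same factor.

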5.1 Atopic dermatitis

AD is a chronic inflammatory skin disease, often referred to as eczema and characterized by widespread skin lesions, manifested as red, itchy, swollen, cracked, weeping lesions with crusting/scaling, intractable itch (pruritus), and enhanced susceptibility to bacterial and viral skin infections. Persistent itch that often causes sleep deprivation and disfiguration of the skin substantially impairs patients' quality of life (1, 2). In a subset of patients, onset of AD precedes that of other conditions such as food allergies, asthma, and allergic rhinitis in a pattern known as the atopic march (3). AD has a worldwide lifetime prevalence of 15 to 20% in children (4) and up to 10% in adults (5, 6) and its prevalence has increased 2- to 3-fold during the past 3 decades in industrialized countries (5). Pathophysiology of AD is complicated and regulated by several genetic and environmental factors. However, it is believed to be mainly driven by Th2 cell responses (7, 8).

Itch can be defined as an unpleasant cutaneous sensation associated with the immediate desire to scratch and has been attributed to increased release of various itch mediators such as histamine. Itch is known to be a common symptom in dermatologic and systemic diseases (9). Although numerous substances such as substance P, serotonin, IL-31, and tryptase are known to cause itch, histamine is also well known to evoke itch when applied to the skin (10, 11).

Itch is a primary symptom of AD and can occur both during the day and at night. Nocturnal itch can significantly impact a patient's sleep and quality of life (12, 13). Nocturnal scratching can lead to difficulties falling asleep and frequent awakening (14). The resulting fatigue and difficulty concentrating can prevent the patient from fully engaging in school, work, hobbies, and socially (15). In addition, persistent scratching can lead to secondary impacts of AD such as decreased skin barrier function and increased risk of infection, as well as disfigurement, scarring, and other complications (16, 17).

Treatment recommendations for AD include topical treatments, mainly TCS. However, not all patients with moderate to severe AD are adequately treated with TCS and TCI. TCS and oral systemic treatments (e.g. cyclosporine, azathioprine) are all associated with toxicities when used in the long-term (18-20). Therefore, patients with moderate to severe AD experience a high unmet need for alternative AD treatments.

Since histamine levels are highly elevated in inflamed skin (21), it is possible that histamine is involved in inflammatory skin pathology. However, antagonists blocking H1R or H2Rs are largely ineffective in reducing chronic symptoms of AD (22, 23). H4R was discovered in the early 2000s and various selective H4R antagonists have allowed understanding the expression and function of the H4 receptor (24, 25). Research on H4R has shown that H4R antagonists have anti-pruritic and anti-inflammatory effects in inflammatory mouse models (26, 27) and in clinical trials in AD (28, 29). Therefore, H4R may present a novel therapeutic target in AD.

